6.2 Preparation/Handling/Storage/Accountability

6.2.1 Acquisition and Accountability

Acquisition: L9LS and the normal saline placebo will be shipped from the US to the study site where administration will take place, in compliance with all FDA, US Department of Transportation, and United Nations transport guidelines for shipping biohazardous materials.

Accountability: The study pharmacist will be responsible for maintaining an accurate record of the study arm codes, inventory, and an accountability record of study agent supplies. Electronic documentation as well as paper copies may be used.

The empty vials and the unused portion of a vial will be discarded in a biohazard containment bag and incinerated or autoclaved in accordance with the regulatory, institutional or pharmacy policy. Any unopened vials that remain at the end of the study will be returned to the production facility or discarded at the discretion of the manufacturer in accordance with policies that apply to investigational agents. Partially used vials will not be administered to other subjects or used

for *in vitro* experimental studies. These vials will be disposed of in accordance with regulatory, institutional or pharmacy policy.

6.2.2 Formulation, Appearance, Packaging, and Labeling

L9LS was manufactured under current Good Manufacturing Practice (cGMP) by the Vaccine Clinical Materials Program (VCMP) operated under contract by Leidos Biomedical Research, Inc., Frederick, MD. It is a sterile, aqueous, buffered solution that is filled into single -dose vials at 150 + 15 mg/mL to a target fill volume of 2.25 mL in a 3-mL vial. The formulation buffer is the same as the drug substance (DS). The drug product container closure system consists of Type I glass vials, chlorobutyl rubber stoppers, and seals purchased from approved manufacturers. Any diluent composition will be described in the IND. The placebo product will be sterile isotonic (0.9%) normal saline. The products will be prepared by an unblinded pharmacist and placed in a sterile syringe when preparing for SC administration. Because L9LS has a slight yellow tint, and the placebo (normal saline) is colorless, the pharmacist will cover all syringes with transparent yellow tape to maintain blinding. L9LS is more viscous than normal saline, so the study agents will only be administered to subjects SC by designated individuals who remain separate from the team of blinded investigators who conduct all subsequent follow-up study assessments.

Vials of L9LS and placebo will be individually labeled with the name of the material, volume, lot number, concentration, storage instructions, Investigational Use Statement ("Limited by Federal Law to Investigational Use"), and manufacturer information.

6.2.3 Product Storage and Stability

L9LS: L9LS vials should be stored frozen at -35° C to -15° C in a qualified, continuously monitored, temperature-controlled freezer. The site pharmacist must promptly report any storage temperature excursions outside of the normal allowance for the storage device to the IND sponsor. The affected product must be quarantined in a separate area under protocol-specific temperature ranges until further notice from the sponsor. If the excursion results in thawed material, DO NOT REFREEZE; store the thawed, vialed material at 2°C to 8°C.

When a storage/shipping/handling excursion occurs, the IND sponsor designee must send a notification of the occurrence of an excursion to [contact]. An automatic email reply will be sent to the notifier, including (as an attachment) the Clinical Excursion Reporting Form, which can be filled electronically (or manually and scanned, if needed). The completed form and relevant attachments (e.g., temperature charts) must be emailed to the VRC via the same email address ([contact]) using the "reply" function. The IND sponsor will notify the site pharmacist if continued clinical use of the product is acceptable or will provide further instructions.

Prior to preparation for SC administration, thaw and equilibrate vials for a minimum of 90 minutes at ambient temperature (15°C to 32°C). If thawed vials are removed from 2°C to 8°C, equilibrate at ambient temperature for a minimum of 30 minutes. 33

After product preparation in a syringe, the prepared L9LS may be stored at 2°C to 8°C for a maximum of 24 hours and/or at ambient temperature (15°C to 32°C) for a maximum of 4 hours. Product may not be stored in direct sunlight. 33

Placebo: Normal saline will be stored at room temperature in a controlled room per product standards.

6.2.4 Preparation

Study product will be prepared by an unblinded pharmacist. For Part 1, dosing will be weight-based and the pharmacist will prepare one or two syringes to deliver doses of 5 mg/kg, 10 mg/kg, and 20 mg/kg. For those receiving 20 mg/kg L9LS, 2 mL syringes will be used so that a maximum of two injection sites will be used for those requiring up to 600 mg L9LS.

For Part 2, three fixed doses of L9LS will be prepared depending on the participant's weight band, as shown in Table 2. Because L9LS has a slight yellow tint, and the placebo (normal saline) is colorless, the pharmacist will cover all syringes with transparent yellow tape to maintain blinding.

Table 2. Dosing of L9LS (10 to 20 mg/kg) by weight of child for part 2

| L9LS 10 to 20 mg/kg | | | | | | | | |
|------------------------|------------------------|----------------------------|--|--|--|--|--|--|
| Subject weight (kg) | Total dose, mg L9LS | Effective dose in mg/kg | | | | | | |
| 5.00-7.50 | 75 | 10-15 | | | | | | |
| 7.51-15.00 | 150 | 10-20 | | | | | | |
| 15.01-22.50 | 225 | 10-15 | | | | | | |

Weight data from a household survey in the study area indicated that the mean weight for children between 4 and 5 years = 15.7 kg (boys), with 95% of weights falling below 20 kg; thus, we do not anticipate any children <59 months will weigh >22 kg.

For the extension phase (year 2), dosing will be constrained to be within a 20–40 mg/kg range to test higher average doses for ADA and increase the chances for high efficacy, given the known dose-response relationship with mAbs. Depending on the child's weight, one of three dosing bands will be selected, as shown in Table 3.

Table 3. Dosing of L9LS (20 to 40 mg/kg) by weight of child for the extension phase

| L9LS Extension 20–40 mg/kgmg/kg | | | | | | | |
|---------------------------------|------------|---------------------|--|--|--|--|--|
| Subject weight, kg | Total dose | Total volume, mL | | | | | |
| 6 – 7.4 | 225 | 1.5 | | | | | |
| 7.5 – 14.9 | 300 | 2.0 | | | | | |
| 15 – 30 | 600 | 4.0 | | | | | |

Note: given current weights of part 2 participants, no child is expected to weigh more than 30 kg during the extension phase.

For each injection order, the dose level and study arm code will be included in the pharmacy order. To prepare an injection, the pharmacist will follow the IP Preparation SOP.

6.3 Measures to Minimize Bias: Randomization and Blinding

6.3.1 Randomization

Randomization lists for each randomized phase of the trial will be generated by the study statistician, and the randomization code lists will be maintained by a designated pharmacist at the study site where the study intervention will take place.

Randomization is further described in section 9.5.1.

6.3.2 Blinding

Parts 1 and 2, as well as the follow-on (part 1 b and part 2 extension), of this trial will be conducted with a double blind. Because L9LS has a slight yellow tint, and the placebo (normal saline) is colorless, the pharmacy team will cover all syringes with transparent yellow tape to maintain blinding for all parts of the study. The subjects, the clinical staff, and the study team will be blinded to study treatment allocation, with the exception of designated individuals who administer the study agents and remain separate from the team of blinded investigators who conduct all subsequent follow-up study assessments. The study pharmacy team will be unblinded, and they are responsible for maintaining security of study treatment assignments.

Data will remain blinded until the last subject completes the final study visit for each phase of the study (part 1, part 1b, part 2, and the follow-on). Blinded subjects will then be informed about their study treatment assignment.

Unscheduled unblinding, either intentional (e.g., in the case of a medical emergency in a subject) or unintentional, will be handled according to SOPs. Intentional and unintentional unscheduled unblinding will be documented in the appropriate source and/or research record and will include the reason for the unscheduled unblinding, the date it occurred, who approved the unblinding, who was unblinded, who was notified of the unblinding, and the plan for the subject.

The principal investigator will report all cases of intentional and unintentional unscheduled unblinding to the DSMB in writing within 1 business day after site awareness via email to the DSMB mailbox ([contact]) outlining the reason for the unblinding and the date it occurred. The report will also be submitted to the IRBs. If an SAE has resulted in unblinding, this information will be included in the SAE Report.

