Part 2 extension: Assuming there are no safety signals from the day 7 review following dosing children with 30 and 40 mg/kg of product, and prior to the last study visit of the original protocol described above (September 2022 to June 2024), study participants who remain enrolled in the part 2 efficacy study will be invited to participate in a 12-month extension of the study. A separate written consent process will take place. Enrolled children will continue in the same study groups as in part 2: 1 dose L9LS, 2 doses L9LS, or placebo. A dose (of L9LS or placebo) will be given at the start of the extension and again after six months. Those receiving L9LS will receive a dose between 20 and 40 mg/kg, still in a double-blinded fashion. The monthly visit and sample collection schedule will mirror that in part 2.

Objectives:

Primary Objectives:

Part 1:

1. Safety: To evaluate the safety and tolerability of L9LS administered at doses of 5 mg/kg, 10 mg/kg, and 20 mg/kg by SC administration to healthy Kenyan children.

Part 1b:

1. Safety: To evaluate the safety and tolerability of L9LS administered at doses of 30 mg/kg and 40 mg/kg by SC administration to healthy Kenyan children

Part 2:

1. Safety: To evaluate the safety and tolerability of L9LS administered at doses of 10-20 mg/kg by SC administration to healthy Kenyan children.

2. Efficacy: To assess the efficacy of two doses of L9LS at a concentration of 10-20 mg/kg, administered SC to participants aged 5-59 months of age against first/only Pf malaria infection diagnosed by blood smear microscopy (irrespective of fever) over 12 months compared to placebo.

Secondary Objectives:

- 1. To assess the efficacy of one dose of L9LS at 10-20 mg/kg against first/only Pf malaria infection diagnosed by blood smear microscopy over 3 and 6 months compared to placebo.
- 2. To assess the efficacy of one dose of L9LS at 10-20 mg/kg against first/only Pf malaria infection diagnosed by blood smear microscopy over 12 months compared to placebo.
- 3. To evaluate the efficacy of L9LS at 10-20 mg/kg against first/only Pf malaria infection as detected by PCR over 3, 6 and 12 months compared to placebo.
- 4. To assess protection of L9LS at 10-20 mg/kg against clinical malaria (first/only and all episodes) at 3, 6 and 12 months compared to a placebo.
- 5. To assess the primary objective and secondary objectives 1-4 among children 5-17 months of age.

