Participants in part 1 of this study will receive one or two SC injections for a total dose of 5, 10, or 20 mg/kg of L9LS or placebo. Participants in part 1b will receive one or two SC injections for a total dose of 30 or 40 mg/kg.

Participants in part 2 of this study will receive 10-20 mg/kg of L9LS or placebo as a single dose, given in 1 or 2 SC injections, depending on the total dose required. At 6 months after the initial injection, participants who received an initial dose of L9LS will either receive a second L9LS SC injection or a placebo injection. (Those in the placebo arm will receive a second injection of placebo.)

In the part 2 extension study, the investigational product will be administered as two SC injection(s) of either L9LS at a dose of 20–40 mg/kg or matching placebo at the beginning of

year 2 extension and after 6 months.

Study Duration: 36 months (including extension phase).

3 months (part 1 or 1b) or 13 months (part 2) or 26 months **Participant Duration:**

(part 2 plus extension phase).

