For the follow-on study, participants who consent will be enrolled once they complete 12 months of follow-up for part 2. They will receive another antimalarial treatment course and two weeks later they will receive their third dose of either L9LS or placebo; six months later, they will receive a fourth dose of L9LS or placebo. Participants will get the same product (L9LS or placebo) that they received in part 2. They will continue to have monthly study visits until the end of the study (12 months following dose 3). These follow-up visits will assess both safety and efficacy measures.

The study will provide information on the safety and usefulness of L9LS as a therapy used in the prevention of malaria.

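### Section 6.3.2, read naturally, discloses part 2 arms while children who keep those arms are still in an extension promised to be double-blind; continuing children need an exception

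*Combined protocol and SAP*

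**What the plan says.** - **Unblinding rule (section 6.3.2).** Data stay blinded "until the last subject completes the final study visit for each phase of the study (part 1, part 1b, part 2, and the follow-on". The next sentence reads: "Blinded subjects will then be informed about their study treatment assignment".
- **Blinding promised for the extension.** Section 6.3.2 also says that "the follow-on (part 1 b and part 2 extension), of this trial will be conducted with a double blind". The abstract (section 1.1) says "Those receiving L9LS will receive a dose between 20 and 40 mg/kg, still in a double-blinded fashion", and section 4.2.1 commits the extension to a double-blind design.
- **Arms carried over.** The abstract says "Enrolled children will continue in the same study groups as in part 2: 1 dose L9LS, 2 doses L9LS, or placebo". The lay summary (section 1.2) says "Participants will get the same product (L9LS or placebo) that they received in part 2". Sections 4.1.1 and 6.1.1 agree.
- **Timing.** The abstract invites families "prior to the last study visit of the original protocol described above (September 2022 to June 2024"). Section 1.4.4, footnote 0, requires extension pre-enrolment within 3 months of the part 2 Day 364 visit, and the schedule puts extension Day 0 14 to 21 days after pre-enrolment.
- **Database lock.** Section 9.5 places the unblinding of data at database lock, without tying the lock to a phase or giving a date.

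**The concern.** Because the arm does not change, a family told its part 2 assignment also knows its extension assignment, including whether the child is due one or two further L9LS doses. Section 6.3.2 is not limited to families: it governs when the data are unblinded, so clinical staff and assessors could learn the codes as well.

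Extension safety is compared with placebo (sections 4.1.1 and 9.3). The outcomes open to bias are:

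- 7-day reactogenicity, part of one of the three extension primary endpoints, which relies on symptoms such as pain, tiredness and nausea;
- relatedness of adverse events, judged by the investigator or designee (section 8.4.2.1.2). It is not part of the primary endpoint, but it feeds the pausing and halting criteria in sections 8.4.5 and 8.4.6;
- exploratory clinical malaria, because definition 2 in section 2.2.2.3 can be met on a history of fever together with parasitaemia requiring treatment, and knowledge of the arm may change care-seeking.

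The protocol guards this blind elsewhere. It keeps those who inject the product apart from those who assess outcomes, and requires any unscheduled unblinding to be reported within 1 business day. A scheduled disclosure during the extension would undo that protection and could not be reversed.

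**Working it through.** The plan gives no figure to reproduce. The question is whether the part 2 trigger falls before continuing children finish the extension.

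**Definitions**

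- A = days from the first to the last part 2 final visit.
- L = days from that last visit to disclosure. Not in the documents; 0 and 60 days are used as illustrations.
- g = days from a child's part 2 final visit to extension pre-enrolment: 0 to 91 (3 months).
- w = days from pre-enrolment to extension Day 0: 14 to 21.
- Hence g + w = 14 to 112.
- Dose 4 is at extension Day 168 ± 7. Later visits are timed from the actual Day 168 visit (section 1.4.4, asterisked footnote), so the final visit is Day 364 ± 14.

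**Is every child still in the extension at disclosure?**

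The earliest extension finish after a child's own part 2 final visit is 14 + 350 = 364 days (14 + 364 = 378 without windows). The first child to finish part 2 is the limiting case, so the condition is A + L < 364.

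- *Planned enrolment.* Section 5.7 expects 6 months, so A = 182 and the condition holds for L up to 181. That section's own dates, taken as 1 August 2022 to 28 February 2023, give A = 211 and L up to 152.
- *Outer bound.* 1 September 2022 to 30 June 2024 is 668 days. The earliest part 2 final visit is day 364 − 14 = 350. So A = 668 − 350 = 318, and the condition holds for L up to 45. This is too wide, because it ignores the time part 1 takes first.

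**Calendar check, nominal visit days.** A child dosed on 1 September 2022 closes part 2 on 31 August 2023, starts the extension no earlier than 14 September 2023, and finishes about 12 September 2024. That is 74 to 103 days after a last part 2 visit between 30 June and 1 June 2024. A last child closing on 30 June 2024 would start between 14 July and 20 October 2024.

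**Share dosed after disclosure**, assuming part 2 final visits are spread evenly over A:

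- Dose 3 share = (g + w − L)/A
- Dose 4 share = (g + w + 168 ± 7 − L)/A

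Both are clipped to 0–100%. The numerators at L = 0 run from 14 to 112 (dose 3) and from 14 + 161 = 175 to 112 + 175 = 287 (dose 4). At L = 60 each falls by 60.

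| A | L | Dose 3 after disclosure | Dose 4 after disclosure |
|---|---|---|---|
| 182 | 0 | 14/182 to 112/182 = 8–62% | 175/182 to 100% = 96–100% |
| 182 | 60 | 0 to 52/182 = 0–29% | 115/182 to 100% = 63–100% |
| 318 | 0 | 14/318 to 112/318 = 4–35% | 175/318 to 287/318 = 55–90% |
| 318 | 60 | 0 to 52/318 = 0–16% | 115/318 to 227/318 = 36–71% |

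The number of children is at most 3 × 108 = 324; the footnote to Table 1 says fewer may remain.

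**The case against.** **The other reading.** The sentence can be taken to mean that nothing is unblinded until all listed phases are finished. That would honour the three promises of a double-blind extension. It also fits the participant duration in section 1.1, which gives "13 months (part 2) or 26 months" for part 2 plus the extension, and the single database lock in section 9.5. This stands as a possible reading, but no section states it. Part 2 has its own close-out visit and section 1.4.4 calls the extension a phase. On the alternative reading, part 1 children, followed for 3 months, would wait for the end of a 36-month study. If it is the intended meaning, the text still has to say so, because staff following 6.3.2 as written could disclose.

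**The interim analysis.** Section 9.5.8 plans a 24-week efficacy analysis before the part 2 trigger, so the blinding sentence is not strictly literal and arm-level analysis is already distinct from telling families. True, but that analysis sets no rule for continuing children.

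**Unknown timing.** The lag is not given, both values of A are weak, and even spacing is assumed. This stands: the shares in the table are illustrations and do not pin down the exposure.

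**Limited impact.** With L = 60, at least 71% (A = 182) or 84% (A = 318) of children would receive dose 3 still blinded, and some early children would receive dose 4 blinded as well. Clinical malaria needs a positive smear, and routine smears are read by two independent microscopists. Serum L9LS and ADA are little affected, extension efficacy is exploratory, and part 2 primary efficacy is untouched. Consent is little exposed, since section 5.7 invites families before their last part 2 visit; only late finishers using the 3-month allowance could learn their arm first. All of this stands and limits the weight of the point.

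**Conclusion.** The concern holds and should be fixed. Applied as naturally read, the rule in 6.3.2 breaks the blind that the same section promises for the extension, and nothing in the protocol prevents it. On planned enrolment, every child who completes the extension would still be in it, or not yet dosed in it, for any lag up to about 6 months (181 days); on the outer-bound dates, up to 45 days. Beyond those lags the earliest finishers drop out of the affected group, but others remain.

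The conclusion rests on the phase-by-phase reading. The 364-day result uses the schedule's own windows; the values of A, the lag and the even spread are assumptions. The effect falls mainly on subjective safety reporting, particularly around dose 4.

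**What to change.** Add an exception to section 6.3.2: for part 2 children who enter, or may still enter, the extension, individual assignments stay concealed from families, clinical staff and outcome assessors until the last extension visit. A separate unblinded team can analyse part 2 on time and report it by arm only. If the intended meaning is already that all listed phases must finish first, state that explicitly for these children.

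The cost is protocol wording and keeping the part 2 analysis team apart from extension assessment. If the last part 2 child joins the extension, continuing families would learn their arm 14 + 364 = 378 to 112 + 364 = 476 days after the last part 2 visit (14 + 350 = 364 to 112 + 378 = 490 with visit windows), instead of soon after it.

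As a separate tidy-up, the extension schedule in section 1.4.4 marks randomization at extension Day 0. That should be reconciled with the carried-over arms in sections 1.1, 1.2, 4.1.1 and 6.1.1. The conclusion here does not depend on it.

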6.4 Study Intervention Compliance

Study intervention administration will be documented by study staff.

6.5 Concomitant Therapy

All concomitant prescription and nonprescription (including over-the-counter, herbal, or traditional) medications taken during study participation will be recorded. For this protocol, a prescription medication is defined as a medication that can be prescribed only by a properly authorized/licensed clinician.

Treatment with the following drugs and procedures will not be permitted unless discussed with and approved by the investigator:

- Live or killed vaccines within 2 weeks of study agent administration. (In Kenya there are no routine vaccinations scheduled for 5- to 10-year-old children; see Appendix A)
- Immunoglobulins for the duration of the study.
- Receipt of any investigational product or co-enrollment in other clinical studies of investigational products.
- Oral or IV corticosteroids at immunosuppressive doses (i.e., prednisone >10 mg/day for 6 or more days) or immunosuppressive drugs for the duration of the study.

Patients taking any of the following drugs at the time of enrolment will be excluded due to the potential for prolongation of the QT interval when used concomitantly with DP. These drugs will not be prohibited at other time points in the follow-up period.

- Antimicrobial agents of the following classes (systemic use only):
 - Macrolides (e.g. erythromycin, clarithromycin, azithromycin, roxithromycin)
 - Fluoroquinolones (e.g., levofloxacin, moxifloxacin, sparfloxacin)
 - Pentamidine
- Antiarrhythmic agents (e.g. amiodarone, sotalol)
- Antihistamines (e.g. promethazine)
- Antifungals (systemic): ketoconazole, fluconazole, itraconazole
- Antiretrovirals: Saquinavir
- Diuretics (e.g. hydrochlorothiazide, furosemide)
- Antipsychotics (neuroleptics): haloperidol, thioridazine
- Antidepressants: imipramin, citalopram, escitalopram
- Antiemetics: domperidone, chlorpromazine, ondansetron

